Control Group:	Subjects in the control group will undergo a standard procedure for catheter-based VT ablation.				
Primary Endpoint:	
 
Time to first event requiring appropriate ICD therapy for ventricular arrhythmia or Incessant VT (VT occurring below the ICD rate cut-off)
 
				
Secondary Endpoints:	
 
Appropriate ICD therapy for ventricular arrhythmia
 
Appropriate ICD Shocks ventricular arrhythmia
 
Inappropriate ICD therapy
 
All ICD therapy (Appropriate + Inappropriate)
 
A composite of Mortality, ICD storm, and Incessant VT (VT occurring below the ICD rate cut-off)
 
Number of Hospitalizations for Cardiovascular Causes.
 
Total VT burden (Number of episodes).
 
All-Cause Mortality.
 
The occurrence of ICD storm, defined as ≥3 appropriate shock therapies within 24 hours.
 
Differences in blood hormone measurements (including norepinephrine, aldosterone, renin, and BNP).
 
Differences in Cardiac parameters, including LV size (septal and free wall thickness) and mitral inflow (E&A velocity), as measured by trans-thoracic echocardiography.
 
Procedure related adverse events including, but not limited to hematomas, pseudoanuerysms, renal artery stenosis, renal impairment, thromboembolic events, stroke, pericardial bleeding including tamponade and myocardial infarction
 
Change in blood pressure
 
				

	
 
15. Development of orthostatic hypotension
 
16. Other individual complication rates including, but not limited to MI and death.
 
17. 30-day Major Complication Rate defined as death, stroke, MI or any other serious adverse events related to the treatment or procedure within the first 30 days or through hospital discharge (whichever is longer);
 
18. Procedure time
 

Primary Analytical Analysis:	Intent to treat analysis
Secondary Analytical Analysis:	Per protocol analysis
Principal Investigator:	[name]. Mount Sinai School of Medicine [name]
Site, Monitoring, and Data Management Center	Electrophysiology Clinical Research Group Mount Sinai School of Medicine [name]
Data Safety and Monitoring Board:	TBD

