Thus, anti-arrhythmic drugs and catheter ablation each have limitations as sole therapies in patients at risk for recurrent ICD shocks. One adjunctive strategy under investigation is renal sympathetic denervation (RSDN). Recently, RSDN has been developed as a therapy to treat hypertension in patients resistant to anti-hypertensive drug therapy. In the Catheter-Based Renal Sympathetic Denervation for Resistant Hypertension: a multicentre safety and proof-of-principle cohort study, 45 patients with a mean office blood pressure of 177/101 mm Hg (SD 20/15), (mean 4.7 antihypertensive medications) underwent renal sympathetic denervation with radiofrequency based catheter ablation. After the procedure, these patients experienced a mean decrease in office blood pressure of -27/-17 mm Hg at 12 months, as well as a 47% reduction in renal noradrenaline spillover. In the Renal Sympathetic Denervation in Patients with Treatment-Resistant Hypertension (Symplicity HTN-2) Trial, a multi-center prospective trial that

randomized 106 patients to RSDN or medical management, at 6 months, 84% of patients who underwent renal denervation had a reduction in systolic blood pressure of 10 mm Hg or more, compared with 35% of controls (p<0.0001).

RSDN is thought to decrease blood pressure by a number of mechanisms including its ability to favorably affect whole body norepinephrine spillover and decrease central sympathetic tone. Indeed, RSDN has been shown to reduce whole body norepinephrine spillover by 42%, and efferent muscle sympathetic nerve activity by 66%. Interestingly, increased catecholamine and sympathetic activity are both important factors in the development of ventricular arrhythmias. In addition, chronic hypertension is believed to mediate pathogenesis and progression of cardiac arrhythmias via its remodeling effects on cardiac anatomy through the renin-angiotensin-aldosterone system.

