# 4. Schedule of Treatment and Tests:

TABLE 1: SCHEDULE OF	Baseline	Procedure*	Discharge	1 month	6,12,18 & 24 months
Type of visit	Office	Hospital		Office	Office or Transtelephonic
Informed Consent	Х				
Brief History & Physical	Х			Х	
Blood Laboratory Testing: CBC, Electrolytes, BUN/Creatinine, BNP	Х				X (12, 24m)
NIH Stroke Scale	Х		Х		
Blood for Renal Hormones (OPTIONAL)	Х				X (12m)
ТТЕ	Х				X (12 m)
Renal Angiography		Х			
Ultrasound or MR/CT Angiography					X (6 m)
Randomization		Х			
Renal Sympathetic Denervation		Х			
ICD Interrogation/remote transmission	Х			Х	X
EKG	Х				X (12m)
Office BP Measurements (including orthostatic BPs)	Х			Х	X (12m)
Medications	Х		Х	Х	Х
Adverse Events		X	Х	Х	X

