# 5.2: Secondary Endpoints:

The following secondary endpoints will be assessed:

- 1) Appropriate ICD therapy for ventricular arrhythmia assessed in the full intention-to-treat patient cohort
- 2) Appropriate ICD Shocks for ventricular arrhythmia
- 3) Inappropriate ICD therapy
- 4) All ICD therapy (Appropriate + Inappropriate)
- 5) A composite of Mortality, ICD storm, and Incessant VT (VT occurring below the ICD rate cut-off)
- 6) Number of Hospitalizations for Cardiovascular Causes.
- 7) Total VT burden (Number of episodes).
- 8) All-Cause Mortality.
- 9) The occurrence of ICD storm, defined as  $\geq 3$  appropriate shock therapies within 24 hours.
- 10) Differences in blood hormone measurements (including norepinephrine, aldosterone, renin, and BNP).
- 11) Differences in BUN/creatinine measurements.
- 12) Differences in cardiac parameters, including LV size (septal and free wall thickness) and mitral inflow (E&A velocity), as measured by trans-thoracic echocardiography.
- 13) Procedure related adverse events including, but not limited to hematomas, pseudoanuerysms, renal artery stenosis, renal impairment, thromboembolic events, stroke, pericardial bleeding including tamponade and myocardial infarction.
- 14) Development of orthostatic hypotension
- 15) Changes in blood pressure
- 16) Other individual complication rates including, but not limited to MI and death.
- 17) 30-day Major Complication Rate defined as death, stroke, MI or any other serious adverse events related to the treatment or procedure within the first 30 days or through hospital discharge (whichever is longer);
- 18) Procedure time

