### 9. Pre-Procedure and Ablation Study Design Flow-Chart

#### **PRE- AND ABLATION PROCEDURE**

### 9.1.1 **PRE-PROCEDURE**

The following tests and procedures will occur before the ablation:

- Recording of patient medical history (including details of VT both clinical/ICD)
- Recording medication history (including all AAD ever used, duration of use)
- Obtain β-HCG in females of child bearing age the morning of the procedure as per usual clinical practice
- Baseline assessment of arrhythmia burden and type: Office/inpatient records, ICD interrogation report
- Baseline NIH stroke scale
- If performed for any reason, collect any pre-procedural imaging: MRI/CT and Renal Ultrasounds within 6 months of procedure
- Baseline laboratory, including complete blood count, standard electrolyte panel, renal function, and brain natriuretic peptide levels.
- Baseline Transthoracic Echocardiogram
- Baseline blood pressure. Proper blood pressure measurement technique is essential: i) patient should sit quietly in a chair with his/her back supported for 5 minutes before taking the measurement; ii) use of the correct cuff size with the air bladder encircling at least 80% of the arm (the adult large cuff for the majority of patients); iii) support the arm at heart level during the cuff measurement; iv) a minimum of 2 readings should be taken at intervals of at least 1 minute and the average of those readings should be taken to represent the patient's blood pressure; v) the blood pressure should be measured
- Consent must be obtained before the VT ablation procedure.
- Randomization into one of two groups will be performed by opening the Randomization envelope after Renal Angiography.

Study/Experimental Group: These subjects will undergo catheter-based sympathetic renal denervation.

Placebo Control Group: These subjects will receive no further intervention..

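### Secondary endpoints 10, 11, 12 and 15 are named as a change or as undefined differences, with no baseline adjustment or main visit stated, although the baseline values are collected

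*Combined protocol and SAP*

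**What the plan says.** Section 5.2 lists 18 secondary endpoints by name. Four of them are continuous measures that also have a scheduled baseline value:

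- Endpoint 15: "Changes in blood pressure" (in the Protocol Summary, "Change in blood pressure").
- Endpoint 10: "Differences in blood hormone measurements (including norepinephrine, aldosterone, renin, and BNP".
- Endpoint 11: "Differences in BUN/creatinine measurements".
- Endpoint 12: "Differences in cardiac parameters, including LV size (septal and free wall thickness) and mitral inflow (E&A velocity".

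For none of these does the text give the visit, the scale, the model or the covariates. For endpoints 10 to 12 it does not say whether the difference is between arms at follow-up or from baseline. The table of contents lists no statistical analysis section. The only analysis statements, in the Protocol Summary and section 5, concern which patients are analysed.

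The baseline data are there. In Table 1 (section 4) the row "Office BP Measurements (including orthostatic BPs" is marked at baseline, 1 month and 12 months. BNP and BUN/creatinine are marked at baseline, 12 and 24 months, echocardiography at baseline and 12 months, and renal hormones, as an optional sample, at baseline and 12 months. Section 9.1.1 confirms this with "Baseline laboratory, including complete blood count, standard electrolyte panel, renal function, and brain natriuretic peptide levels", a baseline echocardiogram and a standardised blood pressure technique.

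**The concern.** Read at face value, the list uses two unadjusted metrics. A change score subtracts the whole baseline value, as if follow-up tracked baseline with a slope of 1. A raw follow-up difference ignores the baseline, as if that slope were 0. With equal variances the real slope is the baseline/follow-up correlation, which normally lies between the two. Each metric therefore carries avoidable variance, and each leaves part of any chance baseline imbalance in the estimate.

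These endpoints matter to the trial's argument. The rationale section rests on lower sympathetic tone, lower catecholamines, less renin-angiotensin-aldosterone activity and ventricular remodelling, which endpoints 10 and 12 would show. Endpoint 15 follows blood pressure, and endpoint 11 follows renal function after a procedure whose listed risks include renal dysfunction. With no model stated, an analyst holding the data could report the raw, the change or the adjusted estimate, and these can disagree within one trial.

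**Working it through.** **1. The plan's own figure.** Section 7 gives 83 per arm for 65% against 85% success, 80% power and two-sided alpha 0.05. With a mean proportion of 0.75:

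- n = [1.96·√(2·0.75·0.25) + 0.8416·√(0.65·0.35 + 0.85·0.15)]² / 0.20² = (1.2002 + 0.5015)² / 0.04 = 72.4
- With continuity correction: (72.4/4)·[1 + √(1 + 4/(72.4·0.20))]² = 82.1, rounded up to 83

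So 83 reproduces. It is a size for the primary endpoint, and none is given for the continuous endpoints. I use 83 per arm as the number with data. For the optional hormones that is too high.

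**2. Formulas.** Let r be the correlation between baseline and follow-up, with the same SD at both times. In units of 2·SD²/n, the large-sample variance of the treatment effect is 1 for a raw follow-up difference, 2(1−r) for a change score and 1−r² for analysis of covariance (ANCOVA). The ratios are therefore ANCOVA/change = (1+r)/2 and ANCOVA/raw = 1−r².

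**3. Variance ratios.** The documents give no correlation, so r is assumed and shown over a range.

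| r | Change | ANCOVA | ANCOVA/change | ANCOVA/raw |
|---|---|---|---|---|
| 0.3 | 1.40 | 0.91 | 0.65 | 0.91 |
| 0.5 | 1.00 | 0.75 | 0.75 | 0.75 |
| 0.7 | 0.60 | 0.51 | 0.85 | 0.51 |

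In patient numbers, a change score needs 1.54, 1.33 and 1.18 times as many patients as ANCOVA, and a raw difference 1.10, 1.33 and 1.96 times. These ratios do not depend on n or on the SD.

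**4. Illustration for systolic pressure.** The only SD in the documents is in the Introduction: "mean office blood pressure of 177/101 mm Hg (SD 20/15". It comes from 45 patients with resistant hypertension, so it is an assumption here. With SD 20, the standard error of a raw difference is 20·√(2/83) = 3.10 mm Hg. The difference detectable at 80% power is 2.802 × 3.10 = 8.7 mm Hg, multiplied by the square root of the variance factor for the other methods:

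| r | Raw | Change | ANCOVA |
|---|---|---|---|
| 0.3 | 8.7 | 10.3 | 8.3 |
| 0.5 | 8.7 | 8.7 | 7.5 |
| 0.7 | 8.7 | 6.7 | 6.2 |

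These scale with the SD. At r = 0.5 the detectable difference is 0.4349 SD unadjusted and 0.3766 SD adjusted, which gives 6.5 and 5.6 mm Hg at SD 15, and 10.9 and 9.4 mm Hg at SD 25.

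**5. Chance imbalance.** The standard error of the baseline difference between arms is √(2/83) = 0.155 SD, so 1.96 × 0.155 = 0.30 SD is the edge of its 95% range. An imbalance of that size shifts a raw difference by +0.30·r and a change score by −0.30·(1−r). At r of 0.3, 0.5 and 0.7 that is +0.09, +0.15 and +0.21 SD, and −0.21, −0.15 and −0.09 SD.

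**6. Simulation check.** In 10,000 trials of 83 per arm, at each of r = 0.5 and 0.7, all methods averaged close to zero when there was no effect, so none is biased on average. At r = 0.5 the variances were 0.98 (raw), 0.98 (change) and 0.74 (ANCOVA). The correlation with the baseline imbalance was +0.50, −0.51 and about 0. ANCOVA on the change and ANCOVA on the follow-up value gave the same treatment effect to machine precision.

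**The case against.** The strongest reply is that an endpoint label is not an analysis method. Section 5.2 is a list of names and neither specifies nor excludes adjustment. A change in blood pressure with the baseline value as covariate gives the same treatment estimate as the adjusted follow-up value, so the wording itself loses no precision. This stands, and it limits the point. A reader might infer that the protocol has committed itself to an inferior analysis. It has not: it has stated none.

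Three further stronger readings are not supported either.

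- **That the results would be biased.** Under randomization a chance imbalance is not systematic bias. It affects precision and the estimate in a particular trial.
- **That the loss is known to be large.** The correlation is assumed and the SD is borrowed from another population. This trial has no hypertension criterion, and at r = 0.7 the gain over a change score is only 0.5 mm Hg.
- **That renal safety hangs on this.** Endpoint 13 separately covers renal impairment and renal artery stenosis, and renal imaging is scheduled at 6 months.

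What the reply does not remove is that nothing in the documents provides for adjustment. The direction of the gain does not depend on the assumed correlation: in large samples ANCOVA is never less precise than either unadjusted form.

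**Conclusion.** The point holds in a limited form. For endpoints 10, 11, 12 and 15 the plan names a change or an undefined difference and states neither baseline adjustment nor a main visit, although the baseline values are collected. If they are analysed unadjusted, the variance that ANCOVA would save is 35%, 25% or 15% against a change score, and 9%, 25% or 49% against a raw difference, at r of 0.3, 0.5 and 0.7.

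These figures assume equal SDs at both visits and the stated correlations. The mm Hg figures also assume the SD and 83 patients per arm with data. Four of 18 secondary endpoints are affected. The change is worth making because it costs almost nothing and removes a choice that could otherwise be made after seeing the data.

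**What to change.** Add to section 5.2, for endpoints 10, 11, 12 and 15:

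- **Main visit.** Name one. Twelve months is the visit at which all four are measured.
- **Model.** Compare arms by a model of the follow-up value (or, equivalently, the change) on treatment arm, the same measure at baseline, and site, which is the stratification factor in section 9.1.4. With up to 25 sites and 184 randomized patients, the average is 184/25, about 7 per site, so also state whether site is a random effect or how small sites are pooled.
- **Two follow-up visits.** For blood pressure (1 and 12 months) and for BNP and BUN/creatinine (12 and 24 months), use a repeated-measures model with the 12-month contrast named as the main one.
- **Scale.** Analyse BNP, norepinephrine, renin and aldosterone on the log scale and report ratios of geometric means. That they are right-skewed is an assumption, since the documents give no distribution. It can be checked on pooled baseline data before unblinding.
- **Dialysis.** Section 6.2 allows patients on dialysis to enter, and their creatinine does not measure a renal effect in the same way. For endpoint 11, exclude them or report them separately, defined by dialysis status at baseline so that the randomized comparison is kept.
- **Hormones.** State that sampling is optional and report the number analysed per arm, which will be below 83.

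The cost is a few lines of text, with no new data and no burden on patients. There are two small downsides: a missing baseline needs a simple imputation of the covariate, and log-scale results are read as ratios.

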# 6. STUDY SUBJECTS

# 6.1 INCLUSION CRITERIA

State inclusion criteria for enrollment in study:

Renal VT Version 1.3 November 2012

- 1.  $\geq$  18 years of age
- 2. Structural heart disease (post-MI, dilated cardiomyopathy, sarcoid myopathy, hypertrophic cardiomyopathy, chagas-related cardiomyopathy, etc.)
- 3. Planned for catheter-based ablation of VT
- 4. All patients will have an existing ICD
- 5. Accessibility of renal vasculature (determined by renal angiography)
- 6. Ability to understand the requirements of the study
- 7. Willingness to adhere to study restrictions and comply with all postprocedural follow-up requirements

# 6.2 Exclusion Criteria

Clinical Exclusion Criteria:

- 1) MI or CVA within 30 days
- 2) Coronary Artery Bypass Graft (CABG) within 30 days of this procedure
- 3) Known renovascular abnormalities that would preclude RSDN (eg, renal artery stenosis)
- 4) GFR <30 ml/min (unless receiving dialysis)
- 5) Life expectancy <1 year for any medical condition
- 6) Any condition resulting in a contraindication to anticoagulation (e.g. GI bleeding)
- 7) Inability to give informed consent
- 8) Known pregnancy or positive  $\beta$ -HCG within 7 days of procedure.

# 7. Sample Size Calculation:

We generated our sample size using the following key assumptions:

- 1. In patients receiving catheter ablation for VT alone, the estimated success rate (absence of ICD therapy) at 2 years is 65%
- 2. In patients receiving RSDN in addition to VT ablation, we expect a 30% improvement such that the estimated 2 year success rate is 85%

The power analysis revealed that a 30% improvement in therapy with RSDN would be detected with 83 patients per arm (80% power, 2-sided alpha error of 0.05). This would require an enrollment of a total of 168 patients, with follow-up of 2 years. We expect an ~10% loss to follow-up. Accordingly, we will plan to enroll an additional ~10% of patients so as to have sufficient number of randomized patients: this would require 184 patients. In addition, we expect 10% of patients will have renal vasculature inappropriate for the RSDN procedure (these are patients that will be consented pre-procedure, but will screen out after renal angiography during the VT ablation procedure). Accordingly, we will ultimately plan to include a total of 202 patients: ~18 patients would screen out after renal angiography, and there would remain a total of 92 patients randomized to each arm.

This study is divided into two phases: a PILOT phase (to include 20 patients) followed by the remaining 182 patients to a total of 202 patients. The PILOT phase will be conducted at 2 sites: Homolka Hospital (Prague, Czech Republic) and Mount Sinai Medical Center. An interim safety

[figure not shown]
analysis for the primary endpoint will be conducted when all patients in the PILOT phase (20 subjects) have completed the 1-month follow up visit.

# 8. Patient Enrollment and withdrawal:

This will be a multicenter trial. Patients meeting the study inclusion criteria will be identified in the outpatient or inpatient setting by one of the study sites' primary or co-investigators.

The study will typically be described (including the risks and benefits) during the initial clinic or hospital visit. Consent will typically be obtained at the time of the initial assessment if it is clear that the patient truly understands the nature of the study. Alternatively, the patient will be allowed to take a copy of the consent form home to contemplate whether they would like to be enrolled in the study. A sample consent form can be found in Appendix 1. Only patients who voluntarily provide consent will be included in this study. Consent will be obtained prior to undergoing the ablation procedure. Patients will be able to withdraw from the study at any point without compromising their medical care.

Consent must be obtained before the VT ablation procedure.

### 9. Pre-Procedure and Ablation Study Design Flow-Chart

#### **PRE- AND ABLATION PROCEDURE**

### 9.1.1 **PRE-PROCEDURE**

The following tests and procedures will occur before the ablation:

- Recording of patient medical history (including details of VT both clinical/ICD)
- Recording medication history (including all AAD ever used, duration of use)
- Obtain β-HCG in females of child bearing age the morning of the procedure as per usual clinical practice
- Baseline assessment of arrhythmia burden and type: Office/inpatient records, ICD interrogation report
- Baseline NIH stroke scale
- If performed for any reason, collect any pre-procedural imaging: MRI/CT and Renal Ultrasounds within 6 months of procedure
- Baseline laboratory, including complete blood count, standard electrolyte panel, renal function, and brain natriuretic peptide levels.
- Baseline Transthoracic Echocardiogram
- Baseline blood pressure. Proper blood pressure measurement technique is essential: i) patient should sit quietly in a chair with his/her back supported for 5 minutes before taking the measurement; ii) use of the correct cuff size with the air bladder encircling at least 80% of the arm (the adult large cuff for the majority of patients); iii) support the arm at heart level during the cuff measurement; iv) a minimum of 2 readings should be taken at intervals of at least 1 minute and the average of those readings should be taken to represent the patient's blood pressure; v) the blood pressure should be measured
- Consent must be obtained before the VT ablation procedure.
- Randomization into one of two groups will be performed by opening the Randomization envelope after Renal Angiography.

Study/Experimental Group: These subjects will undergo catheter-based sympathetic renal denervation.

Placebo Control Group: These subjects will receive no further intervention..

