# **PROTOCOL SUMMARY**

Title:	RESET-VT			
Objective:	The goal of this trial is to test the impact of catheter-based renal sympathetic denervation (RSDN) as an adjunctive treatment for patients with either ischemic or non-ischemic cardiomyopathy undergoing catheter ablation of ventricular tachycardia (VT). The proposed study is a prospective, multicenter, randomized control trial. Patients undergoing VT ablation will be randomized to either VT ablation alone or VT ablation + RSDN.			
Design:	This study is a prospective, multicenter, single-blinded, randomized (1:1) control trial evaluating the effectiveness of RSDN in the prevention of recurrent VT in patients with ischemic or non-ischemic ventricular dysfunction who are undergoing catheter ablation for VT. These patients will be randomized to ablation alone or ablation + RSDN. Subjects will only be eligible for this study if they are $\geq$ 18 years of age and have a history of structural heart disease (post-MI, dilated cardiomyopathy, sarcoid myopathy, hypertrophic cardiomyopathy, etc.), have an existing ICD and are planned for catheter-based VT ablation. In addition, eligible patients will have accessible renal vasculature (as determined by renal angiography). The patient will be blinded to the results of randomization. Once randomized, study group subjects will undergo a strategy of catheter-based renal sympathetic denervation + VT ablation. Follow-up will be conducted in regular intervals over a 24- month period.			
Enrollment:	Total: 202 subjects			
	Pilot Phase: 20 subjects (~10 control group, ~10 study group)			
Clinical Sites:	
 
Mount Sinai School of Medicine (PILOT)
 
Homolka Hospital, Prague, Czech Republic (PILOT)
 
Other Sites TBD (total up to 25 sites)
 
			
Time Course:	Initial enrollment: December 2012			
Renal VT Version 1.3 November 2012				

	Last enrollment: July 2013 (Pilot) Last 24-month follow-up: July 2015 (Pilot) Eligible subjects include those ≥ 18 years of age with a history of structural heart disease (post-MI, dilated cardiomyopathy, sarcoid myopathy, hypertrophic cardiomyopathy, etc.), have an existing ICD and are planned for catheter-based VT ablation. In addition, eligible patients will have accessible renal vasculature (as determined by renal angiography).				
Subject Description:					
Study Group:	In addition to VT ablation, the subjects in this group will undergo catheter-based renal sympathetic denervation.				

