#### 9.1.4 RENAL SYMPATHETIC ABLATION PROCEDURAL DETAILS

• In patients randomized to receive RSDN, the procedure will be performed after the VT ablation on therapeutic anticoagulation with intravenous heparin.

- Abdominal aortography will be performed to assess the renal arteries for the suitability of catheter-based renal denervation in all patients. For those patients in whom the angiogram demonstrates that the renal anatomy is inappropriate for the RSDN procedure (small renal arteries, extensive atherosclerosis, renal stenosis, etc), the patient will be excluded from the study as a screen failure. The patient's baseline information will be collected but no further follow-up required (beyond assessing for any adverse events related to the procedure). If the renal arteries are deemed suitable for RSDN, the patient will then undergo randomization.
- Randomization will be done by permuted-block randomization centrally and will be stratified by site. Allocation concealment shall be maintained at all sites by the use of a web-based central randomization scheme. The operating physician controlling the delivery of ablative energy will be aware of the outcome. This approach has been selected to minimize (1) study bias and (2) placebo effect. The randomization schema will be blocked by size for each site.
- After confirmation of eligibility, an irrigated radiofrequency ablation catheter will be introduced sequentially into each renal artery.
- The ablation catheter is placed within a long vascular sheath and advanced into the renal artery. The sheath is advanced over the catheter to engage the renal artery ostium and allow for contrast injection and visualization of the vessel during catheter manipulation.
- After completion of the measurement, no more than six radiofrequency ablation lesions separated both longitudinally and rotationally (a —spid pattern", see figure) will be placed per renal artery. The power will be started at 10 W and titrated to a maximum 20 W, as deemed appropriate by the impedance drop (goal 10% drop). Each lesion should be between 30-120 seconds in duration (no more than 120 seconds per lesion).

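### Section 9.1.1 allocates by envelope while section 9.1.4 requires a central web scheme at all sites, and the order of allocation and VT ablation should be stated outright

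*Combined protocol and SAP*

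**What the plan says.** **Mechanism.** Section 9.1.1 ends its list with: "Randomization into one of two groups will be performed by opening the Randomization envelope after Renal Angiography". Section 9.1.4 describes a different route: "Randomization will be done by permuted-block randomization centrally and will be stratified by site", followed by "Allocation concealment shall be maintained at all sites by the use of a web-based central randomization scheme".

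**Timing.** Section 9.1.4 sends a patient to randomisation once the renal arteries are judged suitable. It also places RSDN after the VT ablation. Section 9.1.1 says that controls have nothing more done to them after allocation. Section 7 describes patients who "will screen out after renal angiography during the VT ablation procedure". The Protocol Summary says: "Once randomized, study group subjects will undergo a strategy of catheter-based renal sympathetic denervation + VT ablation".

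**Blinding.** The design is single-blind. The Protocol Summary says: "The patient will be blinded to the results of randomization". Section 9.1.4 adds that the physician controlling the ablation energy will know the allocation, but does not say from when.

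The section 9 heading refers to a "Pre-Procedure and Ablation Study Design Flow-Chart". That figure was not in the text available to me.

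**The concern.** Two sections give different instructions for the same act. An envelope held at the site and a central web system differ in who holds the next allocation and in what record is left of when it was seen. The protocol relies on the web system for concealment at every site. It describes no safeguards for envelopes and does not say when they would be used. With up to 25 sites planned, sites could allocate differently while each was following the protocol.

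The timing question matters because VT ablation is given in both arms and is left to standard practice (section 9.1.3), so its extent is partly the operator's judgement. If the operator knew the arm before finishing, that judgement could shift. It could shift either way: more ablation in controls because no RSDN will follow, or more in the RSDN arm. Either would act on the primary endpoint, time to first appropriate ICD therapy or incessant VT, and could not be separated from an effect of RSDN. Adjudication of ICD events by the Clinical Events Committee would not remove the difference, because the events themselves would be real.

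**Working it through.** No arithmetic applies. The check is to set the passages side by side.

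**Step 1: can both mechanisms be true?**

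| Element | Section 9.1.1 | Section 9.1.4 |
|---|---|---|
| How the arm is obtained | Envelope opened | Central, web-based scheme |
| Where it applies | No limit stated | All sites |
| Role of the other method | Not mentioned | Not mentioned |

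The sentence "Randomization will be done by permuted-block randomization centrally and will be stratified by site" is not by itself decisive. A permuted-block list stratified by site can be generated centrally and then packed into envelopes. The conflict lies with "Allocation concealment shall be maintained at all sites by the use of a web-based central randomization scheme". Because that sentence covers all sites, the envelope cannot be explained as a method for the two pilot sites or for sites without web access. Nothing makes it a backup. The two instructions do not fit together.

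**Step 2: what triggers allocation?**

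- Section 9.1.1: the renal angiogram has been done.
- Section 9.1.4: the renal arteries have been found suitable.
- Section 9.1.3, on the VT ablation, mentions neither randomisation nor withholding the arm.

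Neither trigger refers to completion of VT ablation. The statement in 9.1.4 that RSDN follows the VT ablation orders the delivery of treatment. It does not order the disclosure of the arm.

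**Step 3: which order does the rest of the text favour?**

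For allocation after VT ablation:
- VT ablation is section 9.1.3. The suitability angiogram and randomisation are set out in section 9.1.4, inside the RSDN sequence.
- Within 9.1.4, suitability leads to randomisation and then to the catheter entering the renal artery.
- Controls have nothing further done after allocation, which fits best if their VT ablation is already over.

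For an earlier allocation:
- "Once randomized, study group subjects will undergo a strategy of catheter-based renal sympathetic denervation + VT ablation" taken literally puts VT ablation after randomisation. It may only describe the treatment strategy.
- Section 7 has the angiogram taking place during the VT ablation procedure. That may mean only the same laboratory session.
- The envelope item stands in a list introduced by "The following tests and procedures will occur before the ablation". This carries little weight, because Table 1 puts renal angiography, randomisation and RSDN all in the Procedure column. Table 1 has no row for VT ablation, so it does not settle the order.

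**Result.** Step 1 shows a contradiction. Steps 2 and 3 show an ambiguity in which the later allocation is the more natural reading but is not required by any sentence I could read.

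**The case against.** On the mechanism, the best defence is that the envelope is loose wording left beside the intended web scheme. That may be so, but both sentences are operative and a site has no basis in the text for ignoring one of them.

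On the timing, the opposing case is stronger, and most of it stands. The section 9 flow-chart is where one would expect the sequence to be drawn. A figure missing from the text I read is not missing from the plan. The layout of 9.1.4 and the description of the control arm both point to allocation after VT ablation, and each contrary passage has an innocent reading. What is left is a case for stating the order in words. It is not a demonstrated fault.

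A reader might go further and infer that the protocol discloses the arm before or during VT ablation. The documents do not support that: no sentence directs it, and the balance of the text is against it. A reader might also want a figure for the resulting bias. One could calculate how large an imbalance in outcome would distort the test, but that would apply to bias from any source. It would also need an assumed test, since the documents name none, and it would say nothing about whether or how far operators would change their practice. A presumption that any bias favours RSDN is equally unsupported.

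**Conclusion.** The contradiction in mechanism holds with high confidence and rests on the text alone: 9.1.1 and 9.1.4 cannot both be followed, and following 9.1.1 bypasses the only concealment method named. This does not show that concealment has failed at any site. It shows that the protocol permits a departure from its own method.

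The timing point holds in a limited form, with medium confidence, and is subject to what the flow-chart shows. The order should be explicit because blinding is stated only for the patient and, apart from the timing of allocation, the readable text gives no means of keeping the arm from those performing the VT ablation. The direction and size of any bias cannot be determined from the documents. A clear flow-chart would settle the intended order, but it would not cure the envelope conflict or the literal sense of the Protocol Summary sentence.

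**What to change.** 1. Delete the envelope sentence from section 9.1.1 and keep the central web scheme of section 9.1.4 as the only mechanism.
2. Add to section 9.1.4: *The allocation is obtained only after VT ablation has ended, whatever its result, and renal suitability has been confirmed.* The words on result keep acute ablation success from deciding who is randomised.
3. Reword the Protocol Summary sentence on what follows randomisation, and check the section 9 flow-chart, so that both agree with this order.

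The cost is one deletion, one added sentence and one reworded sentence, plus a web login at the end of the ablation. A written statement of order is enough; a technical lock in the web system is not needed to resolve the point. The angiogram can stay where it is, and RSDN already follows VT ablation, so no study procedure moves. The sample size is unaffected, because it rests on the assumed success rates, power and alpha in section 7, none of which changes.
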